Enrollment and Eligibility Screening. Patient eligibility will be established based on the initial screening interview and the review of medical information, including laryngological and neurological examinations. Any subject with neurological (other than SD or dystonic VT in the patient groups), laryngeal, or a history of psychiatric problems will be excluded from the study. All patients will be right-handed, native English speakers according to the standardized Edinburgh Handedness Inventory (Oldfield, 1971), which will be important in examining drug-induced central effects during speech production. Because brain and laryngeal surgery may influence functional brain organization, all patients with a history of brain and/or laryngeal surgery will be excluded from the study. To avoid the possibility of confounding effects of drugs that act upon the central nervous system, patients who receive any medication(s) affecting the central nervous system will be excluded from the study. All patients will be asked to abstain from consuming any alcohol or caffeine (or foods with caffeine such as chocolate) for at least 48 hours before the study visits.

General Study Procedures. Eligible patients will require three visits, including one for the alcohol challenge test and two for sodium oxybate and placebo treatments (**Fig. 1**). At their initial baseline, all patients will be assessed for vital signs (blood pressure, pulse, height and weight); cognitive and

[figure not shown]

Fig. 1. Flowchart of study procedures. ETOH+ alcohol-responsive; ETOH- alcohol-non-responsive.

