executive functions using the Montreal Cognitive Assessment (MoCA); prospective suicidality using the Columbia-Suicide Severity Rating Scale (C-SSRS), alcohol use disorder using NIAAA Recommended Alcohol Questions (Six Question Set) and DSM-5 Alcohol Use Disorder Questionnaire, daytime sleepiness using the Epworth Sleepiness Scale, voice/speech and dystonia symptoms (recordings and rating scales); blood will be sampled for genetic analysis. To reduce the burden to participants, some standardized assessments (Edinburgh handedness inventory) collected under the PI's other protocols within the last 12 months may be used in the same participants who agreed to the use of their data for other research studies. This will be done only in those participants who do not have any major changes in their health history at the time of intake screening for this study compared to the time when they participated in the PI's other protocols.

These evaluations will be repeated after alcohol/drug/placebo administrations, as described below. In addition, a questionnaire on side effects will be completed after administration of alcohol and treatments.

Voice and Speech Symptoms will be assessed using the patient's self-evaluation questionnaire and audio recordings of voice and speech samples. Patients will be

asked to produce various vocal tasks eliciting their symptoms, 20 sentences with high vowel content to elicit ADSD symptoms, 20 sentences with high content of voiceless consonants to elicit ABSD symptoms, and to tell a narrative story. Voice and speech samples will be audio recorded immediately before and after alcohol/sodium oxybate/placebo administrations based on a schedule defined below. Audio recordings will be de-identified, randomized and blindly rated to count the voice breaks as well as to quantify harshness, breathiness, tremor, and hoarseness using a visual analog scale with three gradation indicators along a 100-mm line (normal, modulates voice, offsets voice), with distance in mm denoting the degree of deviancy from normal, as described earlier (Kirke et al., 2016).

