Randomization and Allocation. Following the alcohol challenge, patients will be randomized for the double-blind, placebo-controlled, cross-over study. The randomization will be performed by the MEEI Research Pharmacy and will be blinded for the investigators and patients. The study will be conducted under the existing Investigational New Drug (IND) application granted to the PI by the US Food and Drug Administration (FDA) for the use of sodium oxybate in SD and SD/VT patients (#117,954). Patients will be allocated 1:1 to a treatment sequence #1 of sodium oxybate/placebo or sequence #2 of placebo/sodium oxybate. Jazz Pharmaceuticals, Inc., will provide sodium oxybate and the matching placebo for research purposes, which will be sent directly to the MEEI Research Pharmacy. The placebo will be a clear solution with salty taste that matches the appearance and taste of the drug. Sodium oxybate (1.5 g = 3 ml) of oral solution diluted in 47 ml of water) and the placebo (50 ml) will be formulated in sequentially numbered containers by the research pharmacy in the morning of administration. Both patients and investigators will be blinded until all outcome data are processed and the database is locked at the end of the study. EPIC will be used for study drug dispensing to ensure accurate and complete documentation.

Study drug will be administered by a licensed physician associated with this protocol.

As stated above under the *General Study Procedures* section, all patients will be assessed for their vital signs, MoCA, C-SSRS, side effects, and sleepiness immediately before and 45, 180, 300 min after drug/placebo intake. As a primary outcome measure, voice and speech recordings will be performed at the same time points. Data will be de-identified, randomized, and blindly rated for symptom severity, as described above. Our prior studies have shown that the effects of sodium oxybate (1-1.5 g) in ETOH+ movement disorders are obvious 30-45 min following drug intake and last approximately 3.5-4 hours (Frucht et al., 2005a; Frucht et al., 2005b; Arpesella et al., 2009; Simonyan and Frucht, 2013; Rumbach et al., 2016).

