13. RISKS AND DISCOMFORTS AND MINIMIZATION OF RISKS

Risk is the probability and magnitude of harm or discomfort anticipated as a result of participation in the research.

Minimal risk means the probability and magnitude of harm or discomfort anticipated in the research are not greater in and of themselves than those ordinarily encountered in daily life or during the performance of routine physical or psychological examinations or tests.

a) Describe any risks of harm to subjects and/or anticipated discomfort(s) that are reasonably foreseeable, even if unlikely. Identify the safeguards you will put in place to minimize the occurrence of these risks and discomforts. Risks of harm and discomfort may include: physical harm/discomfort, psychological harm/discomfort, legal harm/discomfort, social harm/discomfort and economic harm.

Response: The daytime oral administration of sodium oxybate may entail the risks of developing dizziness, headache, somnolence, emotionality, and nausea as reported earlier (Frucht et al., 2005a; Frucht et al., 2005b; Arpesella et al., 2009). These side effects, however, have marked individual variability, are dose-dependent, observed within 10 minutes of the drug intake, and typically resolve within 30-40 minutes of dosing. Of these factors, dose is the most critical determinant of side effects. Our clinical experience with administering sodium oxybate in SD and VT patients suggests that the vast majority of these patients tolerate the 1.5 g dose without any side effects, and that, if they do develop side effects, these are extremely short lived.

There is a risk of intoxication from the alcohol that you will be given to drink. Symptoms of intoxication may include a feeling of drunkenness, slurred speech, lack of coordination and concentration, nausea, flushing of your face, or feeling hot.

There may be remote risk of loss of data. We will make every attempt to prevent the privacy and confidentiality risk by replacing personal identifying information with codes and by keeping encrypted digital data on the password-secured computer.

b) If applicable, describe any group harms (i.e. research that focuses on a specific group or population that if the results are disclosed, could harm the group as a whole).

Response: N/A

c) Describe any anticipated circumstances in which a "breach of confidentiality" associated with a mandated disclosure (e.g. reporting abuse to authorities) may occur as part of this study?

Response: N/A

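### The Epworth, the only sleepiness scale the plan names, is poorly suited to tracking acute sleepiness at 45, 180 and 300 minutes after a single dose

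*Combined protocol and SAP*

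**What the plan says.** Section 9 (General Study Procedures) describes a baseline battery that includes "daytime sleepiness using the Epworth Sleepiness Scale". It goes on: "These evaluations will be repeated after alcohol/drug/placebo administrations, as described below". It also provides that "a questionnaire on side effects will be completed after administration of alcohol and treatments". Of the three study visits, one is for the alcohol challenge and "two for sodium oxybate and placebo treatments".

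Section 9 (Randomization and Allocation) refers back to the general procedures and schedules "vital signs, MoCA, C-SSRS, side effects, and sleepiness immediately before and 45, 180, 300 min after drug/placebo intake". No scale is attached to the word for sleepiness there. The same paragraph says that the drug's effects on symptoms "last approximately 3.5-4 hours".

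Section 13 lists "risks of developing dizziness, headache, somnolence, emotionality, and nausea" for daytime dosing. It describes these side effects as "observed within 10 minutes of the drug intake, and typically resolve within 30-40 minutes of dosing", with marked variation between individuals.

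For discharge, Section 9 requires the patient to be stable and within 10% of baseline at the end of the fifth hour. It does not say which measurements the 10% applies to. Section 10 makes voice symptoms the primary outcome and lists no secondary outcomes. Section 12 contains no test of sleepiness.

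**The concern.** A repeated safety measure should be able to move when the effect it monitors occurs. In its standard form the Epworth is a trait measure: it asks about a person's usual tendency to doze in everyday situations. A patient who answers it as worded just before dosing, and again 45 minutes later, has little reason to change the answers even if drowsy the second time.

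Somnolence is one of the few acute effects that the plan names, and the plan gives sleepiness its own place at every post-dose check. If the scale cannot respond, similar flat scores on drug and placebo could be taken as a sign that the dose did not sedate, when the instrument was simply not asking about the present. What is at stake is the quality of one safety measurement, not the efficacy result.

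**Working it through.** No figure in the plan needs reproducing. The check is to trace the sleepiness measure through the document and then ask what it can register.

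1. **Which instrument.** The Epworth is in the baseline battery in Section 9. No other sleepiness scale is named anywhere in the document.

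2. **Whether it is repeated.** The general procedures say that the baseline evaluations are repeated after dosing. The treatment-visit paragraph points back to that text and lists sleepiness beside the MoCA and C-SSRS, both from the same battery. The plain reading is that the Epworth is given at all four time points. The alcohol-challenge text schedules breath alcohol and voice recordings but does not mention sleepiness, so the point is limited to the two treatment visits.

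3. **How many ratings.**
 - Per treatment visit: pre-dose + 45 + 180 + 300 min = 4.
 - Per patient: 4 × 2 visits = 8, of which 3 × 2 = 6 are post-dose.
 - At the enrolment ceiling in Section 5 (4 cohorts × 35 = 140): 6 × 140 = 840 post-dose ratings.

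 The last figure counts forms. It does not measure missed sedation or harm, and no loss of sensitivity can be estimated from the documents.

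4. **What happens between ratings.** The first post-dose rating is 45 min after the pre-dose one and the last is 300 min after it. A person's usual dozing tendency should not change over 5 hours, whether or not the person is sleepy at the time.

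5. **Whether a current-state rating has something to detect at these times.**
 - Side effects typically resolve by 30–40 min, so the 45-min check falls 45 − 40 = 5 to 45 − 30 = 15 min after that.
 - The stated duration of symptom effect is 3.5–4 h, or 210–240 min. The 45- and 180-min checks lie inside it. The 300-min check lies 300 − 240 = 60 to 300 − 210 = 90 min beyond it.

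 Many patients may therefore be back to normal at the scheduled checks. A current-state item would show either that or the exceptions. An unchanged Epworth cannot separate the two.

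6. **Link to discharge and analysis.** If the 10% rule were applied to the Epworth, an unchanged non-zero score s gives (s − s)/s = 0%, which passes. The plan does not say that the rule covers sleepiness, and stability is required separately. Sample size, significance levels and the mixed model do not involve sleepiness.

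**The case against.** The strongest case on the other side has four parts.

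- **The content of the scale is not in the documents.** They say only that it measures daytime sleepiness. If the team uses a version worded for the present moment, the point falls. This stands as a condition. However, the plan names the Epworth without mentioning any modification, and what a named instrument asks is part of what the plan has chosen.

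- **Post-dose use is inferred.** The instruction to repeat cannot be literal, because the battery also includes height, alcohol-use questionnaires and genetic blood sampling, none of which is scheduled post-dose. The separately enclosed monitoring and data-management documents might name another item. This is fair. But if the Epworth was meant for baseline only, the post-dose sleepiness measure is unnamed in the protocol and still has to be specified.

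- **Sedation is already covered.** Side effects are asked about at the same time points, the MoCA and vital signs are repeated, stability is required at hour 5, a physician evaluates anyone who fails a criterion, and patients agree to avoid important decisions for 12 hours. This stands, and it is why the point is minor.

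- **A better scale may find little,** since side effects usually pass before the first check. This limits the gain but does not remove it, for the reason given in step 5 of the check.

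A reader might go further and infer that drowsy patients could be sent home on an unchanged Epworth score. The documents do not support that: the 10% rule is not tied to sleepiness, and the other requirements apply regardless. Nor do they show that the visit schedule misses sedation and needs an earlier check. The side-effect questionnaire can record transient drowsiness, and an extra prompt before the 45-min voice recording would touch the primary measurement.

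**Conclusion.** The point holds as a minor improvement to safety measurement. On the plain reading of Section 9, a scale of usual dozing tendency is the sleepiness measure at all four time points on both treatment visits, and the 6 post-dose ratings per patient can barely respond to a single dose. A shorter current-state item would serve the stated purpose better.

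This rests on two assumptions: that the standard Epworth form is used, and that the post-dose sleepiness check is the Epworth named in the baseline battery. The documents show no unsafe discharge, and the primary outcome, sample size and analysis are unaffected.

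**What to change.** Keep the Epworth once, at baseline, to describe habitual sleepiness. At the four scheduled time points on both treatment visits, use a one-item rating of current sleepiness (for example Karolinska or Stanford), and name it in Section 9. Make the result available to the physician at the hour-5 discharge review as information. A mandatory rule that the patient must be back at the pre-dose rating is not needed: no threshold has been justified, and five hours of testing could shift a single self-rated item by a point even on placebo.

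The cost is one amendment and one short form. Patients already assessed will have a different post-dose instrument, so their sleepiness data should be reported separately. If a present-moment version of the Epworth is already in use, it is enough to say so in the protocol.

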5. SUBJECT INFORMATION

a) Target Enrollment- Specify the number of subjects you plan to enroll and justify why this number is sufficient to achieve adequate power for statistical analysis taking into account anticipated screen failures and drop-outs. Include sample size by cohort if the study has multiple cohorts.

Response: Specific Aim #1: To estimate the number of patients in this study, we reviewed our open-label study, in which sodium oxybate improved voice symptoms in 82.2% (37 out of 45) of ETOH+SD and SD/VT patients (p = 0.001). To our knowledge, no other studies have examined the benefits of sodium oxybate in SD and SD/VT. Using an estimated effect size based on values from this study, a binomial test found that a power of 80% at a significance level of 0.0125 will be obtained with 22 patients for the proposed study. To account for a potential patient dropout based on our prior study, we will recruit up to 35 patients per cohort. The total of recruited patients will be up to 140 (4 cohorts x 35 patients/cohort).

b) If this is a multi-center study and other sites rely on the MEE HSC as the IRB of record, please specify the total number of subjects required by all sites to achieve sufficient power.

Response: N/A

c) Provide justification that the researchers have access to sufficient numbers of eligible subjects to meet target enrollment goals (e.g., researcher's own patients, clinic patients with a specific diagnosis, subjects from previous studies who agree to participate in future studies).

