Alcohol Challenge Test. To determine the reliability and reproducibility of patients' self-reported benefits from alcohol on voice symptom, all patients will undergo the standardized alcohol challenge test for movement disorders (Knudsen et al., 2011; Haubenberger et al., 2013; Voller et al., 2014). Oral ethanol (40%, by volume) will be administered at a total dose of 0.8 g/L of the calculated total body water. It may be mixed into 50 ml of a sugarless, uncaffeinated drink, such as diet Sprite (Watson, 1989). The same dose of alcohol will be administered for the second time 30 min after the first administration. EPIC will be used for alcohol dispensing to ensure accurate and complete documentation. The alcoholic drink will be supplied by the MEEI Research Pharmacy. The test will be performed within fixed hours between 10am-12pm. The patients will be asked to drink their

predetermined amount of alcohol as fast as possible within 5-10 min. The levels of alcohol will be assessed using breath alcohol content (brAC) readings of the breathalyzer at eight time points, including twice before the alcohol challenge and at 15, 30, 45, 60, 120 min after alcohol intake (Haubenberger et al., 2013; Voller et al., 2014). Audio recording of voice and speech samples will be synchronized with brAC measurements and rated as described above.

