d)	What risk classification (taking into consideration the probability and magnitude of harm) is appropriate for the proposed research?						
	□ Minimal Risk	X□Greater than Minimal Risk	□ Unknown				
e)	Explain why you feel	this category is appropriate based on	the definition above (if more than				

minimal risk, describe the likelihood and seriousness of such risks).

Response: The participants will receive, on separate visits, alcohol and sodium oxybate, which is a Schedule III controlled substance. Therefore, the risk is classified as Greater than Minimal Risk. However, the risk of serious adverse events is very low given the low dose of administered sodium oxybate and alcohol.

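### The alcohol challenge states a total dose of 0.8 g/L of body water and then repeats the dose, so the cumulative amount is either 1.6 or 0.8 g/L and nothing settles which

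*Combined protocol and SAP*

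**What the plan says.** Section 9, under Alcohol Challenge Test, sets the dose in two sentences. The first has 40% ethanol "administered at a total dose of 0.8 g/L of the calculated total body water". The second reads: "The same dose of alcohol will be administered for the second time 30 min after the first administration". The same paragraph asks patients to drink their "predetermined amount of alcohol as fast as possible within 5-10 min", without putting a number on that amount or saying whether it covers one drink or both. The Research Pharmacy supplies the drink, and dispensing is recorded in EPIC.

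The test is not optional: "all patients will undergo the standardized alcohol challenge test for movement disorders". Section 5 gives the scale: "The total of recruited patients will be up to 140" (4 cohorts of up to 35).

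Section 13 describes the hazard as follows: "There is a risk of intoxication from the alcohol that you will be given to drink". Because participants receive alcohol and sodium oxybate, it continues: "Therefore, the risk is classified as Greater than Minimal Risk". It then states that "the risk of serious adverse events is very low given the low dose of administered sodium oxybate and alcohol". No alcohol figure appears in section 13.

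Section 12 uses the challenge result to label a patient alcohol-responsive when symptoms change by at least 10% from baseline.

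**The concern.** An instruction for giving alcohol to participants should yield one amount. Here the dose is called a total and is then repeated in full, and the two statements cannot both hold if the total means the amount taken over the test.

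What is at stake is first the exposure of participants. The intended amount is uncertain by a factor of 2, for everyone enrolled, in a study that its own protocol places above minimal risk. Anyone checking adherence, including the external monitor and the DSMB, has no cumulative figure to check against. The reassurance in section 13 depends on the alcohol dose being low, and the reader cannot tell which of two exposures was judged low.

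A lesser consequence is reproducibility. The challenge is presented as a standardised test and supports the 10% responder rule, yet it cannot be repeated from the protocol text alone.

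**Working it through.** **Inputs.** Stated dose: 0.8 g per litre of calculated total body water, labelled a total (section 9). Number of administrations: two, the second equal to the first and 30 min later (section 9). Split between drinks: none stated. The 0.8 g/L is itself an input, so there is no derived figure to reproduce.

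**Reading A: 0.8 g/L is one drink, and that drink is repeated.**
- Per drink: 0.8 g/L
- Cumulative: 0.8 + 0.8 = 1.6 g/L

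**Reading B: 0.8 g/L is the total over two equal drinks.**
- Per drink: 0.8 / 2 = 0.4 g/L
- Cumulative: 0.4 + 0.4 = 0.8 g/L

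**Size of the difference.** Cumulative: 1.6 / 0.8 = 2. Per drink: 0.8 / 0.4 = 2. For a participant with W litres of body water, the cumulative amounts are 1.6 × W g and 0.8 × W g, so the ratio is 2 whatever W is. Amounts in grams or expected blood levels are not given here, because they would need body-water values that the protocol does not supply.

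**Which reading does the wording favour?** The only dose stated before the second sentence is 0.8 g/L, so repeating it gives Reading A. The word 'total' must then mean the whole of one drink. Reading B keeps the ordinary sense of 'total' but needs a per-drink figure of 0.4 g/L that is printed nowhere.

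**Does any other section decide it?**
- Section 7 lists alcohol administration among the procedures, without an amount.
- The rest of section 9 gives no per-drink amount, cumulative amount, or target or maximum breath alcohol level from which the dose could be inferred. By contrast, it specifies sodium oxybate in grams and millilitres per administration (1.5 g = 3 ml, diluted in 47 ml of water).
- Section 12 gives the 10% rule and the correlation with breath alcohol, neither with a dose term.
- Section 13 mentions intoxication and a low dose, without a figure. It therefore contradicts neither reading and supports neither.

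**Number affected.** 4 × 35 = up to 140 recruited.

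**Two minor points in the same paragraph, which carry no weight in the conclusion.** Eight breath-alcohol time points are announced, but 2 before and 5 after make 7, although the list may be meant as partial. The post-intake times do not say which drink starts the clock. If it is the first, the 15-min reading comes before the second drink and the 30-min reading coincides with it.

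**The case against.** The strongest reply is that the paragraph can be carried out as written: give 0.8 g/L, then give it again at 30 min. On that view 'total' is a loose adjective for all the ethanol in one drink. Reading B needs both a split and a number that the text lacks, so this is imprecise wording with a favoured reading rather than two opposed instructions. The test is also described as standardised, with cited sources; a pharmacy supplies the drink; and the consent pages, which might state the amount, are not among the material available. Safeguards exist: alcoholism and high-risk drinking are exclusions, and assessments and a side-effect questionnaire follow the alcohol. Finally, 140 is a ceiling.

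Much of this stands. Reading A is the more literal one, the two readings are not equally supported, and 140 is an upper limit. The consequences for inference are also small. Breath alcohol is measured and recordings are synchronised with it, and the responder rule is a within-patient percentage change, so the label remains interpretable. The within-group comparison of sodium oxybate with placebo does not depend on the alcohol dose.

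It does not remove the problem. The favoured reading delivers twice what the plan itself calls the total. Pharmacy supply and EPIC make ad hoc dosing less likely and document what was dispensed, but they do not define what the protocol authorises. The safeguards carry no dose figure. A protocol should state its own dose, whatever its sources or other study papers may say.

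**Conclusion.** The concern holds, and the text must be corrected. The two dose sentences in section 9 give a cumulative alcohol dose of 1.6 g/L or 0.8 g/L of body water, and 0.8 or 0.4 g/L per drink: a factor of 2 for each of up to 140 participants. The low-dose rationale in section 13 cannot be matched to either figure.

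The arithmetic assumes only that the two drinks are equal, as the plan says. The conclusion that no section settles the matter applies to the protocol text available. It rests on participant exposure, not on any claim of bias, misdosing or an unusable responder label. No view is taken on which dose is right.

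**What to change.** The sponsor should reconcile the two sentences in section 9 by stating both the amount per administration and the cumulative amount over the test. It should then confirm that the risk statements in section 13 refer to that cumulative figure, and amend them if they do not. No dose is proposed here.

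In the same amendment, name the drink from which the post-intake reading times run, and make the announced number of breath-alcohol time points agree with the list.

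The cost is a wording amendment to section 9, and to section 13 if needed. It adds no visits, procedures or participants.
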